2.1 Study Rationale

Rheumatoid arthritis is an autoimmune disease characterized by synovial inflammation and hyperplasia. Activated lymphocytes and macrophages produce various proinflammatory mediators which recruit synovial fibroblasts to the joint and activate them. Proliferation of activated synovial fibroblasts further increases production of proinflammatory mediators and tissue-degrading proteinase such as matrix metalloproteinase-3 (MMP-3), resulting in irreversible destruction of bone and cartilage^{1,2}. The current treatment approaches include conventional, biological, and targeted synthetic DMARDs. However, a high proportion of patients only show a partial response or fail to respond to DMARDs currently on the market even used in combination. Therefore, there is a persistent unmet medical need for novel orally active agents with greater efficacy and equivalent or better safety with an alternative mechanism of action.

Teijin America, Inc., (hereafter referred to as Sponsor) has developed TCK-276 (Laboratory code number: TEI-T01276) as a novel synthetic DMARD with an alternative mechanism of action for the treatment of RA. The Sponsor has conducted the Phase 1 single ascending dose (SAD) study using an orally administered capsule containing 5 mg or 50 mg of TCK-276. The Sponsor thereafter plans to develop TCK-276 using an orally administered tablet containing 10 mg or 25 mg of TCK-276.

TCK-276 is a highly potent, orally active, and selective CDK4/6 inhibitor. Historically, CDK4/6 has been extensively explored as a target for anti-cancer therapeutics, however there is also mechanistic evidence to suggest that CDK4/6 contributes to the pathogenesis of RA³. Cyclin dependent kinase 4/6 is a key regulator at G1/S phase checkpoint in the cell cycle. Cyclin dependent kinase 4/6 forms a complex with D-type cyclins (CycD) and phosphorylates retinoblastoma protein (Rb), leading to depression of transcription factor E2F to accelerate S phase transition^{3,4}. Thus, inhibition of CDK4/6 leads to G1 arrest, and cell cycle progression is attenuated in synovial fibroblasts⁵. In addition to the regulation of cell cycle, CDK4/6 has been reported to mediate the production of MMP-3 and monocyte chemoattractant protein 1 via

Rb-independent and dependent pathways⁶. Cyclin dependent kinase 4/6 likely contributes to the pathogenesis of RA by mediating the proliferation of synovial fibroblasts and the production of MMP-3. The inhibition of CDK4/6 may serve a useful therapeutic strategy for RA patients, particularly those with an inadequate response to existing DMARDs.

This multiple ascending dose (MAD) study will evaluate the safety, tolerability, and pharmacokinetic (PK) of orally administered TCK-276 in both male and female patients with RA.

The study is being conducted to establish a dose range that is well tolerated by the majority of study patients with RA and to provide exploratory data on the potential for the treatment of RA. The results of the clinical study will inform the design and dose selection of subsequent studies.

2.2 Background

2.2.1 Summary of Findings from Non-clinical Studies with Potential Clinical Relevance

[figure not shown]
Pharmacodynamic (PD) studies demonstrated that TCK-276 inhibits CDK4/6 and has minimal potential for off-target kinase activity (Sections 5.1.1.2 and 5.1.2 of the Investigator's Brochure [IB]⁷).

[figure not shown]
Results of *in vitro* pharmacology study using rheumatoid arthritis synovial fibroblasts (RASF) indicated that TCK-276 inhibited proliferation and MMP-3 production of RASF (Section 5.1.1.2.5 and 5.1.1.2.6 of the IB).

Results of *in vivo* pharmacology studies using rat and mouse arthritis models, indicated that TCK-276 at ≥ 15 mg/kg of tested doses was effective in the treatment of arthritis with no effect on bone marrow nucleated cells in rat arthritis model and TCK-276 at doses of ≥ 6.25 mg/kg was effective in the treatment of arthritis and bone destruction in mouse arthritis model (Sections 5.1.1.3.1 and 5.1.1.3.2 of the IB⁷).

Safety pharmacology studies were performed *in vitro* and *in vivo* (cardiovascular, central nervous, and respiratory systems) in rats and monkeys. No untoward effects were observed in these studies.

TCK-276 was not genotoxic based on the absence of mutagenic potential in bacterial reverse mutation, the absence of potential for inducing chromosomal aberration in human lymphocytes *in vitro* and in rat bone marrow *in vivo* (Section 5.3.3.2 of the IB⁷).

Embryo-fetal development studies have revealed evidence for teratogenicity in rats and rabbits and post-implantation loss (embryotoxicity) in rabbits (Section 5.3.5.3 of the IB⁷). In the male fertility study, there were no effects on the reproductive function of males or on early embryonic development when treated males were mated with untreated females (Section 5.3.5.1 of the IB⁷).

Based on the non-good laboratory practice preliminary phototoxicity study (non-good laboratory practice grade), TCK-276 is considered to have no phototoxic potential (Section 5.3.7.1 of the IB⁷).

In summary, the preclinical program supports the clinical development of TCK-276, as a once daily, self-administered, oral product for RA treatment. Collectively, the available data indicate that TCK-276 can be useful in the treatment of RA.

2.2.2 Summary of Findings from Previous Clinical Studies

The first-in-human (FIH) Phase 1 SAD study (Study TCK-276-101) evaluating TCK-276 has completed [REDACTED]; 48 subjects have been orally administered capsules ranging from 5 to 185 mg (geometric mean of $AUC_{0-\infty}$: 39.7 to 2,260 ng·h/mL) once daily (QD). Clinical data from the SAD study of TCK-276 showed no drug-related safety signals (i.e., serious adverse events [SAEs], adverse events [AEs] leading to discontinuation). The plasma exposure levels for TCK-276 linearly increased following escalating TCK-276 administration with the proportion of metabolite (TEI-W00595) to parent remaining similar across dose levels. It was noted that no clinically meaningful differences in PK parameters were observed between fed or fasting states for either TCK-276 or its metabolite.

A detailed description of the chemistry, pharmacology, efficacy, and safety of TCK-276 is provided in the IB.

[figure not shown]
2.3 Benefit/Risk Assessment

The risks of TCK-276 known to date are outlined in Section 2.3.1 and the benefits are outlined in Section 2.3.2. More detailed information about the known and expected benefits and risks and reasonably expected AEs of TCK-276 can be found in the IB.

2.3.1 Risk Assessment

Table 2–1 Risk Assessment

Risk Assessment	

Potential Risk of Clinical Significance	Summary of Data/Rationale for Risk	Mitigation Strategy
Other		
Risk of acquiring an infection with SARS-CoV-2 Risk of spreading a SARS-CoV-2 infection	
SARS-CoV-2 is known to be transmissible via respiratory droplets and any interventions that may potentially increase cough or aerosolization of respiratory secretions of an infected patient may increase risk of spread of disease.	
Described below this Table.

SARS-CoV-2 = severe acute respiratory syndrome coronavirus 2.

There is currently an outbreak of respiratory disease (coronavirus disease 2019 [COVID-19]) caused by a novel severe acute respiratory syndrome coronavirus 2 (SARS-CoV-2).

Food and Drug Administration (FDA)⁸ have issued guidelines that aim to provide recommendations for actions for conduct of clinical studies of medical products during the COVID-19 pandemic. Since the pandemic situation is evolving, guidelines, recommendations, national laws and local restrictions may be changed at a high pace. Given the circumstances of a potentially relapsing pandemic or epidemic situation regarding the spread of COVID-19 in the future, special attention will be paid to protect study patients and site staff involved in the investigations against infection with SARS-CoV-2.

The study intervention, TCK-276, may have the potential for CDK4/6 inhibition and the risk of causing immune suppression is low. Therefore, the risk the study patients to contract a COVID-19 infection will be similar to that of the general population. However, the risk of exposure to infected people cannot be completely excluded as the patients might be exposed in public areas (e.g., commute to the site following the treatment period) and have additional human contact (e.g., with site staff and other patients in the clinical study).

Measures to mitigate the additional risks caused by COVID-19 are:

- This study is going to start enrolling only when the Sponsor and contract research organization (CRO) in collaboration deem it is safe to start the study. In addition, the study will not start until the local containment measures or other safety restrictions linked to the COVID-19 pandemic allow.
- Current national laws and local recommendations for prevention of pandemic will be strictly adhered to.
- Patients will be closely monitored for any signs and symptoms of COVID-19, including fever, dry cough, dyspnea, sore throat, fatigue, and changes of taste and smell throughout the study. Once clinical signs of infection are reported by patients, the Investigator needs to determine whether samples can be collected, and safety data can be recorded on-site. If not, information on AEs and concomitant medications will be obtained via phone calls.
- Confirmation of COVID-19 infection by available approved laboratory standard testing should be conducted at Investigator's discretion. This would include serology testing at Screening and virus testing prior to any Admission.
- The probability of virus transmission will be controlled as much as possible by:
 - Advice for patients to adhere to local requirements for reduction of the public exposure while ambulatory.
 - Asking the potential patients to self-isolate for at least 5 days prior to admission.
 - Contacting patients by phone 1 day prior to every visit for assessing COVID-19 symptoms and signs, and patients will be asked not to attend the site in case of suspected reports. In addition, patients will be asked about any contact with a person who has tested positive for SARS-CoV-2. If applicable, patients will be referred to the local health care system for further follow-up and treatment.
 - Physical distancing and person-to-person contact restrictions will be applied during site visits.
 - Where physical distancing is not possible, face shields will be used by study patients (surgical face mask, and gloves) and staff (for example but not limited to masks, gloves, protectors, and medical suits) if deemed appropriate by the Investigators and site staff and guided by local requirements.
 - Logistical improvements of the site and structural measures of the study site building will be implemented to further improve physical distancing.

- Patients will follow the site policy to mitigate the additional risks caused by COVID-19. All medical measures, risk/benefit, and restrictions associated with COVID-19 screening will be explained by the informed consent for COVID-19 screening, and written consent must be obtained before participating in the clinical study. Patients will be allowed to receive COVID-19 vaccines or boosters during the study period if necessary.

2.3.2 Benefit Assessment

TCK-276 is a highly potent, orally active, and selective CDK4/6 inhibitor as a novel synthetic DMARD with an alternative mechanism of action for the treatment of RA.

The protocol has been designed to minimize the risk to research patients. Patients will be monitored to detect AEs during the study and followed appropriately to ensure resolution of AEs. Sentinel dosing will be employed within the first cohort, and available safety/tolerability and PK data will be assessed after each dose level to determine if it is safe to escalate to the next planned higher dose.

Based on CDK4/6 inhibition mechanism of action, the adverse event of special interest (AESI) will be monitored as described in Section [2.3.1](#).

Given the safety and tolerability profile of TCK-276 in preclinical studies and the SAD study, also in view of the short treatment duration of 7 days, the overall risk to the patients in this study is deemed to be low and the patients cannot derive benefit from short term treatment. The study results will help to further develop TCK-276 as potential treatment for RA patients in future and will guide researchers to plan and design future studies. Therefore, the Sponsor considers that it is medically and ethically acceptable to perform the proposed study.

2.3.3 Overall Benefit/Risk Conclusion

Taking into account the measures taken to minimize risk to patients participating in this study, the potential risks identified in association with TCK-276 are justified by the anticipated benefits that may be afforded to patients with RA.

3 Objectives and Endpoints

Study objectives and endpoints are summarized in [Table 3–1](#).

Table 3–1 **Objectives and Endpoints**

Objectives	Endpoints
Primary 
• To evaluate the safety and tolerability of multiple oral doses of TCK 276 in patients with rheumatoid arthritis (RA)	
• Safety and tolerability endpoints: The following safety and tolerability variables will be recorded at regular intervals during the study:
○ Vital signs measurements: supine blood pressure, pulse, body temperature, and respiratory rate○ Cardiac safety for arrhythmias, abnormalities including PR interval, QRS interval, RR interval, QT interval, and QT interval corrected for heart rate (QTc) (Fridericia's correction [QTcF]) as assessed by 12-lead electrocardiogram (ECG) and cardiac telemetry○ Incidence of laboratory abnormalities: hematology, clinical chemistry, coagulation, and urinalysis○ Incidence and severity of adverse event (AE) and adverse event of special interest (AESI) (i.e., gastrointestinal toxicity and pulmonary symptoms indicative of interstitial lung disease) assessments○ Physical examinations
Secondary 
• To evaluate pharmacokinetic (PK) of TCK-276 and its metabolite (TEI-W00595) in patients with RA after multiple ascending dose (MAD) administration	
• PK endpoints The following PK parameters for TCK-276 and TEI-W00595 will be determined, if calculable:
○ C_{max}: Maximum plasma concentration determined directly from the concentration-time profile (Days 1 and 7)

Objectives	Endpoints
	
○ t_{max}: Time of maximum plasma concentration determined directly from the concentration-time profile (Days 1 and 7)○ AUC_{tau}: Area under the plasma concentration-time curve over a dosing interval, $\tau = 24$ hours (Days 1 and 7)○ AUC_{0-t}: Area under the plasma concentration-time curve up to last measurable concentration (Days 1 and 7)○ AUC_{0-inf}: Area under the plasma concentration-time curve from pre-dose (time 0) extrapolated to infinite time (Days 1 and 7)○ MRT_{last}: Mean residence time up to last measurable concentration (Day 1 only)○ MRT_{0-inf}: Mean residence time extrapolated to infinity (Days 1 and 7)○ $t_{1/2}$: Terminal elimination half-life (Days 1 and 7)○ CL/F: Apparent total body clearance (Days 1 and 7), determined for parent only○ V_z/F: Apparent volume of distribution based on terminal phase (Days 1 and 7), determined for parent only○ Metabolic ratio (MR) for C_{max}: Molar metabolic ratio of C_{max} calculated as $(C_{max} [\text{metabolite}] \times \text{molecular weight of parent}) / (C_{max} [\text{parent}] \times \text{molecular weight of metabolite})$ (Days 1 and 7)○ MR for area under the plasma concentration-time curve (AUC): Molar metabolic ratio of AUC calculated as $(AUC [\text{metabolite}] \times \text{molecular weight of parent}) / (AUC [\text{parent}] \times \text{molecular weight of metabolite})$ (Days 1 and 7)○ C_{trough}: Concentration in a dosing period defined as the pre-dose concentration of the day

Objectives	Endpoints
	
○ R_{acc} (C_{max}): Accumulation ratio based on C_{max}: Calculated as C_{max} on Day 7/C_{max} on Day 1○ R_{acc} (AUC_{tau}): Accumulation ratio based on AUC_{tau}: Calculated as AUC_{tau} on Day 7/AUC_{tau} on Day 1 
The following urinary PK parameters for TCK-276 will be determined in this study:
 
○ A_e: Amount of study drug excreted unchanged in the urine (Days 1 and 7)○ F_e: Percentage of study drug excreted unchanged in the urine (Days 1 and 7)○ CL_r: Renal clearance (Days 1 and 7) 
Other PK parameters will be determined if needed.

Exploratory 
● To evaluate the effect of TCK-276 on disease activity and biomarkers in patients with RA	
● Exploratory endpoints 
The following exploratory disease activity parameters for RA will be assessed:
 
○ American College of Rheumatology (ACR) 20/50/70 response criteria○ Disease activity score 28 (DAS28)○ Clinical disease activity index (CDAI)○ Simplified disease activity index (SDAI) 
The following exploratory biomarkers will be assessed:
 
○ Matrix metalloproteinase-3 (MMP-3)○ Granulocyte macrophage colony-stimulating factor (GM-CSF)○ C-X-C motif chemokine ligand 10 (CXCL10)○ C-C motif chemokine ligand 2 (CCL2)○ Cartilage oligomeric matrix protein (COMP)○ Tumor necrosis factor (TNF)-alpha○ TNF-R1○ Interleukin-6 (IL-6)

4 Study Design

4.1 Overall Design

This is a Phase 1, multi-center, double-blind, randomized, placebo-controlled, MAD study to evaluate the safety, tolerability, and PK of orally administered TCK-276 in both males and females with RA. Blood samples for possible future pharmacogenetic, possible future metabolite assessments, and possible future pharmacodynamic (PD) assessments will be collected.

A total of thirty-two (32) patients with RA will be enrolled in this clinical study. This MAD study will consist of 4 cohorts of 8 patients (6 active treatment and 2 matching placebo, or a 3:1 ratio), each receiving an oral dose of TCK-276 or matching placebo for 7 days (QD under fed condition) as shown in [Figure 1–1](#). The first cohort will be divided into 2 subgroups to implement the sentinel dosing approach. Within the cohort, the first subgroup will consist of 2 sentinel patients; one patient will receive TCK-276, and one patient will receive matching placebo. The second subgroup will consist of 6 patients (5 active treatment, 1 matching placebo). Individual patients in the second subgroup will be dosed at least 72 hours after the first dose of the second patient of the first subgroup following a decision by the Investigators based on all available safety data from the sentinel patients up to 48 hours post-dose. Subsequent cohorts (cohort 2-4) will not include the sentinel dosing approach.

Patients will be admitted to the site from the morning of Day -1 and sequestered for the duration of the treatment (dosing) period. Each patient will receive QD oral doses of either TCK-276 or matching placebo administered as tablets under fed condition in the morning of Day 1 to Day 7. The patients will be discharged on Day 10. The planned dose levels to be tested are 10 mg (Cohort 1), 25 mg (Cohort 2), 75 mg (Cohort 3), and 150 mg (Cohort 4) of TCK-276. Based on the results from the SAD study (5 mg to 185 mg dosing) and the projected clinical effective dose (i.e., 75 mg), 10 mg is selected as the starting dose level in the MAD study. The dose in Cohorts 2, 3, and 4 may be adjusted based on the safety and PK results from the previous cohorts, if necessary. The overall exposure to TCK-276 (in terms of geometric mean area under the plasma concentration-time curve over a dosing interval [AUC_{tau} , $\tau = 24$ hours]) on Day 7 would not be expected to exceed [REDACTED]

[REDACTED]. Further details are presented in [Figure 4–1](#).

[figure not shown]
Dose escalation will only be allowed after blinded assessment of all safety, tolerability, and PK data up to Day 10 from each previous cohort evaluated by Investigators, Medical Monitor, and Sponsor representatives during the Safety Review Committee (SRC) meeting.

All patients (including patients who terminate the study early) will return to the site 13 days after the first TCK-276 or TCK-276 matching placebo administration for follow-up procedures and for the end of treatment examination.

Duration of patient participation from the Screening Visit to the end of treatment examination will be approximately 42 days. This includes 27 days for the Screening period, 11 days for the in-house Treatment period (patients will be confined from the morning of Day -1 until all safety assessments have been completed on Day 10), and 4 days after the end of the Treatment period, for the Follow-up/EOT Visit.

If the Investigator, the Sponsor, or the Medical Monitor becomes aware of conditions or events that suggest a possible hazard to patients if the clinical study continues, the clinical study may be terminated after appropriate consultation between the involved parties. The clinical study may also be terminated at the Sponsor's discretion in the absence of such a finding.

Figure 4-1 Study Flow Chart – Multiple Ascending Dose Design

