Patients will be admitted to the site from the morning of Day -1 and sequestered for the duration of the treatment (dosing) period. Each patient will receive QD oral doses of either TCK-276 or matching placebo administered as tablets under fed condition in the morning of Day 1 to Day 7. The patients will be discharged on Day 10. The planned dose levels to be tested are 10 mg (Cohort 1), 25 mg (Cohort 2), 75 mg (Cohort 3), and 150 mg (Cohort 4) of TCK-276. Based on the results from the SAD study (5 mg to 185 mg doses) and the projected clinical effective dose (i.e., 75 mg), 10 mg is selected as the starting dose level in the MAD study. The dose in Cohorts 2, 3, and 4 may be adjusted based on the safety and PK results from the previous cohorts, if necessary.

Dose Group	Treatment Assignment	
1	10 mg TCK-276 (N = 6)	Placebo (N = 2)
2	25 mg TCK-276 (N = 6)	Placebo (N = 2)
3	75 mg TCK-276 (N = 6)	Placebo (N = 2)
4	150 mg TCK-276 (N = 6)	Placebo (N = 2)

[figure not shown]
Data Monitoring/Other Committee:

A SRC will be appointed for this study. The SRC meeting will take place to review safety and PK data during each dose level. The SRC will evaluate the safety and tolerability data up to Follow-up/EOT Visit and available PK data up to Day 10 to determine the next dose for the subsequent cohort.

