4.3 Justification for Dose

In the SAD study, which included dose-levels up to 185 mg (capsule), TCK-276 was generally safe and well tolerated in healthy subjects with no reports of SAEs nor discontinuations due to AEs. The starting dose for the MAD study (10 mg, tablet) is sufficiently lower than the highest dose in the SAD study (185 mg, capsule), and the projected clinical effective dose (75 mg) that was calculated from nonclinical pharmacological study using the rat adjuvant-induced arthritis model.

Patients with RA will be enrolled in this MAD study. Given the data for recently approved RA drugs, an up to 2-fold increased exposure in patients with RA compared to healthy subjects was taken into consideration as a conservative approach. Even if a 2-fold higher exposure in patients with RA would occur, the exposure of the 10 mg in the MAD study corresponds to 20 mg in healthy subjects, which is sufficiently lower than that of the highest dose in the SAD study (185 mg) and the projected clinical effective dose (75 mg).

Therefore, 10 mg as tablet formulation is considered the appropriate starting dose in the MAD study.

The dosing frequency (i.e., QD) was selected considering the PK characteristics of TCK-276 and patient's convenience. The dosing duration (7 days) was considered sufficient to achieve steady state conditions.

Dose Escalation

In this MAD study, the dose escalation progression will be from 10, 25, 75, and up to 150 mg in subsequent cohorts. The overall exposure to TCK-276 (in terms of geometric mean AUC_{tau}) on Day 7 is not expected to exceed the predefined AUC cap [REDACTED]. The exposure at 150 mg dosing in tablet formulation is assumed to be less than the predefined AUC cap based on the results from the SAD study (5 mg to 185 mg, capsule). Therefore, 150 mg is chosen for the highest dose. The dose in Cohorts 2, 3, and 4 may be adjusted based on the safety and PK results from the previous cohorts, if necessary. Dose escalation will only be allowed after blinded assessment of all safety, tolerability, and available PK data up to Day 10 from each previous cohort evaluated by Investigators, Medical Monitor, and Sponsor representatives during the SRC meeting.

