7.1.1 Overall Study Stopping Criteria

The study will be stopped if any of the following occur and are thought to be at least possibly related to study intervention agreed upon by the SRC:

- Two patients develop the same Grade 3 AE (grading is based on the Common Terminology Criteria for Adverse Events [CTCAE] version 5.0).
- One patient develops \geq Grade 4 AE (CTCAE version 5.0).
- Death of a patient at any time.

If any of the following scenarios occur within a cohort with reasonable possibility of a causal relationship with study drug, dosing will be stopped, and further dosing will not be initiated.

- One or more patients experience increased alanine ALT or AST $> 3 \times$ ULN with total bilirubin (TBL) $> 2 \times$ ULN or increased AST $> 3 \times$ ULN accompanied by alkaline phosphatase (ALP) $> 1.5 \times$ ULN.
- One or more patients experience a decrease of absolute neutrophil count less than 1,000/mm³ or white blood cell (WBC) less than $2.5 \times 10^3/\mu\text{L}$ or platelet count less than 75,000/ μL .
- One or more patients have an increase of more than 60 ms in QTcF compared to the baseline QTcF (baseline QTcF = value obtained on Day 1 at pre-dose in the treatment period) or QTcF > 500 ms or other clinically significant conduction disturbance or arrhythmia. All ECGs for this determination must be performed under strict resting conditions.
- Two or more patients, who receive study intervention, have tachycardia defined as resting supine heart rate > 125 beats per minute (bpm) persisting for at least 10 minutes.
- Two or more patients, who receive study intervention, have symptomatic bradycardia defined as resting supine heart rate < 40 bpm accompanied with symptoms of bradycardia while awake persisting for at least 10 minutes.
- Two or more patients, who receive study intervention, develop hypertension defined as an increase in resting supine systolic blood pressure (BP) > 40 mmHg to above a reading of 180 mmHg and persisting for at least 10 minutes.

If the criteria were met, the SRC will carefully review the totality of data, considering moderate non-serious AEs at least possibly related to the study intervention administration in unblinded

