7.1.2 Dose Escalation

After each sub-cohort and cohort, the Principal Investigator and the SRC will evaluate the safety, tolerability data and available PK data up to Day 10 to determine the next dose. The predefined AUC_{tau} [REDACTED] level will be used in the SRC as a benchmark so that the human exposure can be compared with preclinical exposure data. The safety and PK data from all patients in the previous cohort must be reviewed before a decision to escalate the dose can be made. Dose escalation will only occur if data from a minimum of 6 patients have been reviewed from the previous lower dose group, such that data from a minimum of 4 patients who have received active treatment will be used to make the dose escalation decision (based on the randomization of 6 active treatment:2 matching placebo).

Doses will not exceed a dose level at which the geometric mean of AUC_{tau} exceeds or would be anticipated to exceed the following limits:

[REDACTED]

[REDACTED]
[REDACTED]
[REDACTED]
[REDACTED]

If PK data indicate that the predefined AUC [REDACTED] has been achieved or would be exceeded with escalation to the next higher dose, dose escalation will be stopped. A dose in which the stopping criteria have been met will not be repeated and further dose escalation will not occur. Where stopping criteria have not been met, the decision of the SRC may be to give the next intended dose, a smaller than the predefined dose increment, a repeated dose or to stop dosing. The SRC will make the decision for the next dose level (to give the next intended dose, a greater or smaller dose increment than the intended dose, a repeated dose) or whether to stop the study after reviewing all the pertinent safety and any other relevant data and decision of the voting members. If consensus among the voting SRC members cannot be reached then the Principal Investigators, who have the ultimate responsibility for the safety of the patients, will make the final decision on the next dose level or whether to stop the study. In any event, dose escalation can only occur if agreed by the Principal Investigators. The decisions of the SRC on the next dose level will be documented and provided to all the appropriate parties

involved with the study, including the pharmacist to enable study intervention preparation for the next scheduled dosing day.

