Initially the data will be reviewed blinded, but if the Principal Investigators or the SRC consider it necessary due to a safety concern, either individual patients or the entire cohort may be unblinded to enable decision making. Before breaking the code, the potential decisions and actions should be determined. The code will be broken according to local standard operating procedures (SOPs). Following review of data from a cohort of patients, the timing of assessments and/or blood samples may be adjusted for subsequent cohorts.

Dose escalation will be stopped if any of the following occur and are thought to be at least possibly related to study intervention agreed upon by the SRC. It is determined that the limit of safety and/or tolerability has been reached as determined by the SRC.

- Two or more of the patients in a cohort develop \geq Grade 2 AEs (CTCAE version 5.0) in the same category, related to TCK-276, as judged by the Investigator.
- One or more patients in a cohort develop \geq Grade 3 AEs (CTCAE version 5.0) in the same category, related to TCK-276, as judged by the Investigator.

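### The safety cut-off for dose escalation is Day 10 in some sections and the Day 14 follow-up visit in others, and nothing says which governs

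*Protocol*

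**What the plan says.** Two versions of the rule appear, and both the protocol and the SAP contain each of them.

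- **Day 10 for everything.** Protocol 4.1: "Dose escalation will only be allowed after blinded assessment of all safety, tolerability, and PK data up to Day 10 from each previous cohort". The same sentence stands in the synopsis (1.1, Overall Design) and in SAP 3.1.
- **Day 14 for safety, Day 10 for PK.** Protocol 1.1, Data Monitoring/Other Committee: "The SRC will evaluate the safety and tolerability data up to Follow-up/EOT Visit and available PK data up to Day 10", for the purpose of choosing the next dose. SAP 4.13.10 repeats it.

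Other sections do not settle the matter.

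- Protocol 4.3 inserts one word: "Dose escalation will only be allowed after blinded assessment of all safety, tolerability, and available PK data up to Day 10".
- Protocol 7.1.2, the section on escalation, says that "the SRC will evaluate the safety, tolerability data and available PK data up to Day 10 to determine the next dose". In both places the day may limit PK only.
- Protocol 7.1.2 adds that "The safety and PK data from all patients in the previous cohort must be reviewed before a decision to escalate the dose can be made", but gives no day for the safety data. It also sets a floor of 6 reviewed patients, at least 4 of them on active drug.
- Protocol 1.2 and 4.2 mention the SRC review without a day. SAP 4.21, which lists changes to the planned analysis, is silent.

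**The concern.** The SRC review comes before every dose increase. After Cohort 1 it is the main check before a full cohort is exposed, because the protocol says: "Subsequent cohorts (cohort 2-4) will not include the sentinel dosing approach".

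The cut-off day decides which events the escalation rules can count. Under 7.1.2, escalation stops if "Two or more of the patients in a cohort develop" related Grade 2 or higher events in the same category, or if one patient has a related Grade 3 or higher event. Under 7.1.1, dosing stops if "One or more patients experience a decrease of absolute neutrophil count less than" 1,000/mm³ with a reasonable possibility of a causal link. Myelosuppression is an adverse event of special interest (8.4.6). A second Grade 2 event on Day 12, or a low neutrophil count first found on Day 14, would count under one version of the rule and not yet be visible under the other.

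The study is multi-center and the Principal Investigators sit on the SRC (10.1.5). Members could convene on either day and each cite approved text.

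**Working it through.** The plan gives no figure to reproduce. The check is a comparison of the texts and a count of study days.

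**Can one reading reconcile the sections?**

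- *Day 10 limits PK only, everywhere.* This is possible in 4.3 and 7.1.2, where the word for availability attaches to PK. It is strained in 4.1, the synopsis Overall Design and SAP 3.1, where one phrase covers safety, tolerability and PK together.
- *Day 10 is only a minimum.* An SRC that waits for Day 14 then meets both versions. But 4.1 does not mention the later visit, so an SRC that relies on 4.1 alone is not told to wait for it.

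**Inputs.** Last dose: Day 7. Discharge: Day 10. The follow-up visit is 13 days after the first dose (4.1), so Day 1 + 13 = Day 14. Assessment days come from Table 1-1 and its footnotes 3 and 4. Adverse events are collected through Day 14 (8.4.1).

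**Follow-up after the last dose at the time of review.** Day 10 − Day 7 = 3 days. Day 14 − Day 7 = 7 days. Difference = 4 days.

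**What has been seen for a patient who has just reached the cut-off**

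| Item | Cut-off Day 10 | Cut-off Day 14 |
|---|---|---|
| Adverse-event days from first dose | 10 of 14 | 14 of 14 |
| Adverse-event days after last dose (Days 8–14) | 3 of 7 | 7 of 7 |
| Hematology days after first dose (4, 7, 8, 9, 10, 14) | 5 of 6 | 6 of 6 |
| ECG days after the last dosing day (8, 9, 10, 14) | 3 of 4 | 4 of 4 |
| Scheduled full physical examination after dosing starts (Day 14) | 0 of 1 | 1 of 1 |

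The unseen calendar time is 4/14 = 29% of the days from first dose and 4/7 = 57% of the days after the last dose.

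**Who is affected.** The table describes the last patients dosed in a cohort; earlier entrants are further along. In Cohort 1 the second subgroup starts at least 72 hours (3 days) after the second sentinel's first dose. When that subgroup reaches Day 10, the sentinels are at Day 10 + 3 = Day 13 or later.

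**Dose steps at the three uses of the rule.** 25/10 = 2.5; 75/25 = 3.0; 150/75 = 2.0 at the protocol's top dose, or 175/75 = 2.33 at the SAP's.

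**The case against.** The best defense is that the texts can be obeyed together. The sentence in 4.1 sets a condition that must be met before escalation; it does not say that escalation may go ahead without Day 14 data. Section 7.1.2 also calls for safety data from all patients, with no cap. This stands in part. A reader might infer that the two rules cannot both be followed, or that the plan intends escalation without the follow-up visit; the documents support neither. What remains is that the design section names an earlier day than the SRC paragraph, and nothing ranks them.

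A second defense is practical. Day 10 is the day of the last PK sample, 72 hours after the Day 7 dose. That sample must be assayed and the exposure compared with the AUC limit before the SRC decides. If this takes four days or more, most or all of the gap closes. That is fair, but no turnaround time is given, and 4.3 and 7.1.2 ask only for PK data that are available.

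Third, safeguards exist. Five of six hematology days fall by Day 10. The Day 10 brief examination can be extended to a full one (8.3.1). Single doses up to 185 mg showed no drug-related safety signal (2.2.2). The 7.1.1 rules and 24-hour AESI reporting stay active. These lower the stakes but do not replace the visit: reporting starts only once the investigator learns of an event, and a symptom-free fall in neutrophils after discharge has no scheduled test before Day 14. The earlier study gave single doses, not seven daily ones.

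Finally, the SAP repeats protocol wording and does not govern dosing; SAP 3.1 still describes sentinels in every cohort. Its two passages are copies to be aligned, not independent evidence.

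**Conclusion.** The inconsistency is real and should be corrected. A stated safety decision rule has two cut-offs that differ by 4 days, and no section resolves them. The exposure is limited: an SRC relying on 4.1 alone could escalate before the last-dosed patients' Day 14 hematology, ECG, full physical examination and Days 11 to 14 adverse events are reviewed. This could arise at each of three escalations of 2.0- to 3.0-fold.

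Two stronger inferences should be resisted.

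- A reader might infer that the next cohort could start on Day 11 and receive several doses before the Day 14 visit. The documents do not support that as a realistic case. Section 4.1 itself makes Day 10 PK part of the review, the SRC must meet and its decision must reach the pharmacist (7.1.2), and patients are admitted on Day −1, which for a Day 11 start would be the previous cohort's Day 10.
- A reader might take 29% or 57% as the share of risk that goes unseen. They are shares of calendar days; the plan gives no event rate and none is assumed here.

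The conclusion rests on Table 1-1 as scheduled. How often the gap would open depends on the unstated PK turnaround.

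**What to change.** State one rule in protocol 1.1 (Overall Design), 4.1, 4.3 and 7.1.2, and in SAP 3.1, using the stricter version already in the synopsis SRC paragraph and SAP 4.13.10:

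- No patient in the next cohort is dosed until the SRC has reviewed the previous cohort's safety and tolerability data through the Day 14 Follow-up/EOT Visit and available PK data through Day 10.
- Day 14 data are needed from at least the 6 patients that 7.1.2 already requires. With 2 placebo patients in 8, this guarantees 6 − 2 = 4 active without unblinding.
- For the other patients, including anyone who missed the visit or terminated early, all available safety data are reviewed. One missed outpatient visit then cannot stall the study, and the all-patients sentence in 7.1.2 is still honored.

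The cost is about 4 days per escalation, about 3 × 4 = 12 days over three, and less if PK assay time already delays the SRC meeting. No visit or sample is added. If the sponsor does intend Day 10 for safety, it should instead change the synopsis SRC paragraph and SAP 4.13.10 and justify the shorter follow-up.
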